5.0 CRITERIA FOR SUBJECT ELIGIBILITY

Describe the characteristics of the subject population.

5.1 Subject Inclusion Criteria

- Female participant must be scheduled for a total laparoscopic or robotic-assisted hysterectomy for a gynecologic condition
- Female participants must be 18 years of age or older

5.2 Subject Exclusion Criteria

 Female participant is not eligible if the surgeon does not plan to use a uterine manipulator

6.0 RECRUITMENT PLAN

Potential research subjects will be identified by a member of the patient's treatment team, the principal investigator, or a member of the research team. If the treatment team member is an investigator on the research study, s/he will screen their patients' medical records for suitable research study participants and contact those patients to discuss the study and the potential for enrolling in the study. If the treating physician is not a study investigator and identifies potential subjects, the patients will be contacted by their treating physician and will be referred to the investigator/research staff of the study.

Potential study participants who meet our basic inclusion/exclusion criteria will be approached by their physicians to volunteer for this study. If the patient indicates a willingness to participate, an investigator will explain the study in detail. The goal is to obtain 40 patients undergoing surgery from at least 8 of the 12 GYN surgeons. The Research Study Assistant (RSA) will maintain a sign-up sheet to track the surgeries scheduled to use the robotic manipulator, as only one device is available. The maximum number of robotic uses per surgeon will be 8. This will allow us to obtain a representable sample of responses regarding the robotic manipulator and its utility.

7.0 ASSESSMENT/EVALUATION PLAN

After obtaining informed consent, data regarding the patient's treatment and disease status will be abstracted from the medical record for the purpose of characterizing the sample. Data will be collected regarding the disease stage, surgical characteristics, and patient demographics.

During the surgery, the surgeon will note any intraoperative complications. These are recorded on the operative report. The operative report is synoptic. Nomenclature and severity of grading for intraoperative complications is standardized. The surgeon or fellow will also note the feasibility of docking the V-Care uterine manipulator. If the robot cannot be docked with the V-Care and does not stay securely in place, the reason will be recorded.

After surgery, the surgeon will complete the product evaluation form and deliver it to the RSA. The evaluation form asks questions to determine ease of use, specifically, whether manipulation with the BAUM was successful, whether the device was successfully docked, the occurrence of any complications, and how easy it was to use. Patients will be followed by the study team for 25-35 days after surgery to track any postoperative complications

related to the robotic device. The complications will be tracked in the study database. There are no anticipated additional risks above what can be experienced during the scheduled surgery performed without the BAUM. If a complication occurs, [name] and/or the treating physician will review to determine if it is attributable to the use of the BAUM. Attribution determination will be made based on the type of complication and whether it is a medical or anesthetic complication of surgery, for example surgery complications may include bleeding or infection. Participants will be monitored for all complications for 25-35 days post surgery. If the standard-of-care post-operative visit is outside of the 25-35 day window, a clinician will call the patient during the 25-35 day window and document any post-operative complications.

8.0 TOXICITIES/SIDE EFFECTS

There are no anticipated additional toxicities associated with study participation other than the standard risks of utilizing a uterine manipulator. Those include uterine perforation and vaginal laceration.

9.0 PRIMARY OUTCOMES

The primary outcomes for this study are feasibility, safety, and utility of the BAUM device. Feasibility will be determined by whether successful docking of the BAUM is achieved and if the manipulation of the uterus was successful for the duration of the procedure. Safety will be measured by the number of intraoperative complications attributed to the robotic device during surgeries using this manipulator. Utility will be measured by the product evaluation form provided by the Department of Perioperative Services.

All outcomes will be assessed by the attending surgeon during the total laparoscopic or robotic-assisted hysterectomy. Successful or unsuccessful docking of the robotic manipulator with the V-Care, and any intraoperative complications related to the robotic manipulator will be recorded on the product evaluation form. Utility will be assessed using an 8-item questionnaire on the product evaluation form. This form must be completed by the attending surgeon upon completion of the case.

10.0 CRITERIA FOR REMOVAL FROM STUDY

Patients will be removed from the study for any of the following reasons and they will be replaced:

- If at any time the patient is found to be ineligible for the protocol as designated in the section on Criteria for Patient/Subject Eligibility (e.g., a change in diagnosis that necessitates an open hysterectomy), she will be removed from the study.
- If the patient decides to withdraw consent or discontinue participation in the study, she will be removed from the study.
- If the use of the BAUM device is abandoned for any reason prior to surgery, the patient will be removed from the study.

If the surgeon is unable to dock the robotic manipulator or if it fails to operate properly during the procedure for any reason, the patient will not be replaced and this reason will be recorded. These patients will be considered as failures for the primary endpoint.

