1.0 PROTOCOL SUMMARY AND/OR SCHEMA

The objective of this study, entitled "Pilot Trial of the Robotic Uterine Manipulator," is to evaluate the feasibility, safety and utility of a newly developed robotic uterine manipulator system. The [name] Automated Uterine Manipulator (BAUM) was developed by [name] in collaboration with the MSK Innovation and Technology Team (ITT) and with the support of the Device Design and Development Fund (3DF). Subsequent funding for the external development by a development engineering partner with an extensive track record in developing medical devices, MPR Inc., has been provided through [name] discretionary funding and institutional donor funding. There will be a single robotic unit available for testing that robotically positions the clinically established and FDA approved V-Care uterine manipulator. Our hypothesis is that use of the BAUM will be feasible in nearly all patients undergoing total laparoscopic or robotic-assisted hysterectomy, will provide sufficient uterine manipulation and will have a low rate of associated intraoperative complications.

All patients undergoing total laparoscopic or robotic-assisted hysterectomy that will include the use of a uterine manipulator would be eligible for participation in this study. Annually, MSK's Gynecology Service performs approximately 500 laparoscopic and robotic-assisted hysterectomies. It is estimated that 90% of these patients would be eligible for this study. The standard protocol accrual rate is 30-35%. We estimate that this pilot study will reach the target accrual of 40 patients in one year or less.

Eligible patients will be consented for the study at the time of their surgical consultation. At the time of surgery, the BAUM prototype will be available for placement, use, and evaluation. The robotic manipulator will be affixed to the V-Care at the start of each case. The V-Care is an FDA approved uterine manipulator which will attach to the investigational BAUM. The V-Care manipulator will be used internally to move or manipulate the uterus to ensure that the surgeon's view is not blocked, so that he or she can perform the surgery effectively and safely, given the nearness of surrounding organs, such as the ureters, bladder, and colon. Historically a clinical staff member was responsible for positioning the instrument according to verbal commands from the surgeon. The BAUM will be utilized in place of a clinical staff member, attaching directly to the V-Care.

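### Section 10.0 replaces patients whose BAUM use is abandoned before surgery even when the device itself is at fault, so the 35-of-40 count can overstate feasibility of intended use

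*Combined protocol and SAP*

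**What the plan says.** Section 10.0 of the combined protocol and SAP opens its list of removals with "Patients will be removed from the study for any of the following reasons and they will be replaced". The third ground reads: "If the use of the BAUM device is abandoned for any reason prior to surgery, the patient will be removed from the study". The list does not separate device-related from other reasons, and no section defines the boundary before surgery.

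The paragraph after the list treats a second group differently. "If the surgeon is unable to dock the robotic manipulator or if it fails to operate properly during the procedure for any reason", then "the patient will not be replaced and this reason will be recorded", and the patient is a failure for the primary endpoint.

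The count feeds the decision rule in Section 11.0: fewer than 35 successes in 40 leads to re-design and reassessment of feasibility. Section 11.0 does not mention removed or replaced patients.

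Three statements give the context:
- Section 1.0, the aim: "Our hypothesis is that use of the BAUM will be feasible in nearly all patients".
- Section 1.0, availability: "There will be a single robotic unit available for testing" and "At the time of surgery, the BAUM prototype will be available for placement, use, and evaluation".
- Section 6.0, scheduling: the research study assistant "will maintain a sign-up sheet to track the surgeries scheduled to use the robotic manipulator, as only one device is available".

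**The concern.** Section 10.0 accepts that a device which does not perform is a feasibility failure. Its third removal ground withdraws that principle for a fault found slightly earlier. If the only unit malfunctions before docking is attempted and the team proceeds without it, the wording sends the patient to replacement.

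Replacement for a clash over the single unit, or for a change of surgical plan, carries no information about the device and does not bias the count. Replacement because the device did not work does carry such information, and it can move the count in one direction only. Section 10.0 asks for a recorded reason for docking and operating failures but not for abandonment before surgery, so the plan does not ensure that the two kinds of replacement are distinguished in the report.

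At stake is the choice between carrying on with the present design and re-designing it. Section 4.1 adds that an application for FDA approval may follow successful completion.

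**Working it through.** **Inputs.** From Section 11.0: n = 40, threshold 35 successes, expected success 90–95%. The documents give no rate of device-related abandonment before docking, so 0%, 1%, 2% and 5% are assumptions.

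**The plan's own figures.** P(X ≥ 35) for X ~ Binomial(40, p) gives 0.00000, 0.00014, 0.00862, 0.16133 and 0.79373 at p = 0.5, 0.6, 0.7, 0.8 and 0.9. All five match the table in Section 11.0.

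**Illustration on an observed result.** If 35/40 is observed and k replaced patients were device faults, success over all intended uses is 35/(40 + k):

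| k | Success over intended uses |
|---|---|
| 0 | 35/40 = 87.5% |
| 1 | 35/41 = 85.4% |
| 2 | 35/42 = 83.3% |
| 3 | 35/43 = 81.4% |
| 4 | 35/44 = 79.5% |

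**Effect on the decision rule.** Let s be true success among all patients in whom BAUM use was intended, and a the share lost to device faults before docking and replaced. The 40 who are counted then have success rate s/(1 − a), and P(pass) is the probability that Binomial(40, s/(1 − a)) is at least 35. The expected number replaced while filling 40 places is 40a/(1 − a).

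| a | Expected replaced | s = 0.80: apparent rate | P(pass) | s = 0.70: apparent rate | P(pass) |
|---|---|---|---|---|---|
| 0% | 0 | 0.8000 | 0.161 | 0.7000 | 0.009 |
| 1% | 0.40 | 0.8081 | 0.194 | 0.7071 | 0.011 |
| 2% | 0.82 | 0.8163 | 0.231 | 0.7143 | 0.014 |
| 5% | 2.11 | 0.8421 | 0.379 | 0.7368 | 0.029 |

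At s = 0.80 the failures make up 0.20 of patients, so a = 1%, 2% or 5% means that 0.01/0.20 = 5%, 0.02/0.20 = 10% or 0.05/0.20 = 25% of all failures arise before docking. The last row is a demanding assumption.

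**The other side of the ledger.** Now hold success among attempted dockings at 0.90 and count device-related abandonments as failures. The success rate becomes 0.90(1 − a): 0.900, 0.891, 0.882 and 0.855 at a = 0%, 1%, 2% and 5%. P(≥ 35/40) is then 0.794, 0.733, 0.668 and 0.468.

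**The case against.** The strongest reply is that nothing is biased for the endpoint as defined. Sections 9.0 and 11.0 define feasibility through docking and holding for the length of the procedure, and Section 9.0 has the surgeon assess outcomes during the operation. A patient who never reaches that stage has no such outcome, and the Section 11.0 table is exact for those who do. This stands. A reader might infer that the docking success rate itself is inflated; the documents do not support that. The overstatement is relative to the broader hypothesis in Section 1.0, that use of the device is feasible.

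The second reply is that the gap is narrow. The device is placed at the start of each case (Section 4.2), unsuccessful mounting goes on the evaluation form (Section 1.0), the reason is recorded when the robot cannot be docked (Section 7.0), and Section 10.0 counts inability to dock as a failure. A set-up failure in the operating room may therefore already count. This stands in part: it is a plausible reading, but the any-reason wording of the third removal ground points the other way, and a fault found before the case begins is not covered at all.

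A reader might also infer that replacements for device faults could never be identified afterwards. That goes too far. The sign-up sheet (Section 6.0), source documents (Section 13.0) and registration reports (Section 13.1) may allow it. None of them requires the reason for abandonment, however.

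Lastly, the size is hypothetical, and the trial is a single-arm pilot in which missing the threshold leads to re-design. Both are true, and they limit the weight of the point.

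**Conclusion.** The point holds in a limited form. As written, Section 10.0 allows a device fault before attempted docking to be replaced rather than counted, and no other section restores that patient to the 40 or requires the reason. For feasibility of intended use, the direction of any error is certain: upward. Its size is unknown and is zero if no such case occurs. Under the assumed rates of 1% to 5%, the chance of passing at a true success of 0.80 rises from 0.161 to between 0.194 and 0.379; at 0.70 it stays below 0.03. These figures assume independent patients and a constant abandonment rate.

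The documents do not show that such faults will occur, and they do not make the Section 11.0 table wrong for attempted dockings. The change is worth making because the rule determines the primary count and is easily clarified.

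**What to change.** Amend Section 10.0, with the reason for abandonment as the single boundary:

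1. Limit replacement under the third removal ground to abandonment for reasons unrelated to device function, such as scheduling of the single unit or a change of surgical plan.
2. Count abandonment because the device malfunctions or cannot be set up, at any time before docking, as a failure that is not replaced. Report success among attempted dockings alongside, so that the endpoint of Sections 9.0 and 11.0 stays visible.
3. Record and report the reason for every replacement.

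Basing the rule on the reason removes the need to define exactly when surgery begins. No separate rule for the safety count is needed for this point.

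The cost is one paragraph and one data field, with no extra patients. The downside is real if faults occur: at 90% success among attempted dockings, the chance of reaching 35 falls from 0.794 to 0.733, 0.668 or 0.468 at 1%, 2% or 5% abandonment. One outage of the single unit could also count against several scheduled patients, which departs from the binomial assumption in Section 11.0, so failures from one outage should be reported as linked events.

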11.0 BIOSTATISTICS

The primary aim of the study is to show that the docking of the BAUM is feasible and subsequent uterine positioning is feasible. The BAUM will be considered successfully docked when the V-Care is inserted into the uterus and secured in place to the robotic arm to hold for the duration of the procedure. Interim data will be reviewed and presented.

We expect a very high percentage (90-95%) of patients to achieve successful docking and that the device will be held securely in place for the duration of the procedure. With 40 patients, the 95% confidence interval around a hypothetical 50% success rate is (35%, 65%); if the hypothetical success rate is 90% then the confidence interval is (81%, 99%), assuming binomial proportions. If the number of successes is less than 35 we will warrant re-design of the device and reassessment of its feasibility. The table below provides the probability of observing at least 35 successes (>=35) out of 40 patients under true hypothetical rates of success from 0.5 to 0. 9..

Obs	n	m	р	Prob of seeing >=35	Probability of seeing <35
1	40	35	0.5	0.00000	1.00000
2	40	35	0.6	0.00014	0.99986
				0.000.0	0.00400
3	40	35	0.7	0.00862	0.99138
4	40	35	0.8	0.16133	0.83867
5	40	35	0.9	0.79373	0.20627

Safety will be assessed by reporting all intraoperative complications during the surgery. Complications might include vaginal tear or uterine perforation. The number and type of complications will be reported. Among 554 patients who underwent laparoscopic or robotic-assisted hysterectomy at MSK from 7/1/14-6/30/15, there were 2 patients who experienced 2 true intraoperative complications. There are no expected postoperative complications, as the manipulator is removed following surgery so patients participating in the study will undergo routine follow-up. The study will stop for safety if we observe 2 intraoperative complications out of 40 patients. The table below provides the probability of observing at least 2 complications (>=2) out of 40 patients under true hypothetical rates ranging from 0.05 to 0.2. We expect the complication rate to be much smaller than 0.05.

Obs	n	m	р	Prob of seeing 2 or more	Probability of seeing 1 or less
1	40	2	0.05	0.60094	0.39906
2	40	2	0.10	0.91953	0.08047
3	40	2	0.15	0.98789	0.01211
4	40	2	0.20	0.99854	0.00146

The utility of the BAUM will be assessed by data collected from surgeons using the standard MSK OR new product evaluation form (see Appendix). All data will be reported descriptively. Surgeons will rate the robotic manipulator on different patients. In addition to using the cutoff of 3 or above (acceptable or better), the percentage of robotic uses for which surgeons rated each item as acceptable or better (score of 3, 4, or 5) will be reported for each item separately. Question 8 asks for the surgeon's recommendation for future use of the robotic manipulator. The maximum number of robotic manipulator uses per surgeon will be 8. This will allow us to obtain a representative sample of responses regarding the robotic device and its utility. If there are issues with utility, we will re-evaluate the design of the device to address the concerns.

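### The 95% interval of (81%, 99%) given for a 90% success rate in 40 patients is an unnamed Wald interval; exact or Wilson limits put its lower end about 4 points lower

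*Combined protocol and SAP*

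**What the plan says.** Section 11.0 makes docking the device, and holding the uterus in position with it, the primary aim. It states the expected result: "We expect a very high percentage (90-95%) of patients to achieve successful docking". It then gives two 95% confidence intervals for 40 patients. One, at a hypothetical 50% success rate, is (35%, 65%). The other is at the lower end of the expected range: "if the hypothetical success rate is 90% then the confidence interval is (81%, 99%), assuming binomial proportions". The only description of method is "assuming binomial proportions", which names a distribution and not a way of forming an interval. No other section names one.

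The feasibility decision is stated separately, as a count: "If the number of successes is less than 35 we will warrant re-design of the device and reassessment of its feasibility". A table of the probability of at least 35 successes at true rates from 0.5 to 0.9 supports it. The section does not say whether an interval will accompany the observed success rate, or how it would be calculated.

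**The concern.** At 90% success in 40 patients only 4 failures are expected. The Wald interval is symmetric about the observed proportion and takes its standard error from that same proportion. Close to 100% this places both limits too high.

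The (81%, 99%) interval is the plan's only statement of precision for its primary aim at a success rate it expects to see. A reader would infer that 36/40 rules out a true rate of 80%; exact and Wilson intervals both include 80%. Because the method is unnamed, the same formula could also be carried into the final report, where it behaves worse as the observed rate approaches 100%.

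**Working it through.** **Inputs, all from section 11.0.** n = 40; 95% confidence, two-sided because two limits are printed; hypothetical rate 90%, that is 36/40; expected range 90-95%; pass mark 35/40. z = 1.96.

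**1. Reproducing the plan's figures.** Wald: p ± z·√(p(1−p)/n).
- 36/40: 0.9 ± 1.96·√(0.09/40) = 0.9 ± 0.093, giving 80.7% to 99.3%, printed as (81%, 99%).
- 20/40: 0.5 ± 1.96·√(0.25/40) = 0.5 ± 0.155, giving 34.5% to 65.5%, printed as (35%, 65%).

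For 36/40, Wald with continuity correction (79.5%, 100.5%), Agresti-Coull (76.4%, 96.6%) and Jeffreys (78.0%, 96.5%) do not match the printed limits, and neither do the exact and Wilson intervals below. The printed interval is therefore a correct calculation by the plain Wald formula. The issue is the choice of method.

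**2. Alternative intervals.**
- Wilson: [p + z²/2n ± z·√(p(1−p)/n + z²/4n²)] / (1 + z²/n).
- Clopper-Pearson exact, for x successes: lower limit is the 2.5% point of Beta(x, n−x+1); upper limit is the 97.5% point of Beta(x+1, n−x).

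| Successes | Wald | Wilson | Exact |
|---|---|---|---|
| 36/40 | 80.7-99.3% | 77.0-96.0% | 76.3-97.2% |
| 35/40 | 77.3-97.7% | 73.9-94.5% | 73.2-95.8% |
| 20/40 | 34.5-65.5% | 35.2-64.8% | 33.8-66.2% |

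At 36/40 the Wald lower limit exceeds the exact one by 80.7 − 76.3 = 4.4 points. Against Wilson, the unrounded limits 80.70% and 76.95% differ by 3.8 points. The Wald upper limit is 2.1 and 3.3 points higher respectively. The widths are not very different (18.6 points Wald, 19.1 Wilson, 20.9 exact): the Wald interval is mainly displaced upwards. At 50% the choice hardly matters.

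**3. Behaviour over the expected range.** Coverage at a true rate p is the sum of the binomial(40, p) probabilities of the outcomes whose interval contains p. Computed on a fine grid of p from 0.90 to 0.95:

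| | Wald | Wilson | Exact |
|---|---|---|---|
| Mean coverage | 88.7% | 95.8% | 98.0% |
| Minimum coverage | 79.5% | 93.5% | 95.3% |
| Share of range below 95% | 100% | 31% | 0% |
| Mean chance lower limit is above true rate | 10.8% | 0.5% | 0.5% |
| Mean chance upper limit is below true rate | 0.5% | 3.7% | 1.5% |

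The nominal chance of error on each side is 2.5%. Wald coverage peaks at 94.5% and is below 90% over 59% of the range.

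**4. Comparison with the section's own table.** The success table is exact binomial and reproduces: P(X ≥ 35) = 0.16133 at p = 0.8 and 0.79373 at p = 0.9. By the same calculation, P(X ≥ 36) at p = 0.8 is 7.6%, well above 2.5%. So 36/40 does not exclude 80%, although the printed interval suggests that it does.

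**5. If Wald were also used for reporting.** Upper limits would be 100.7% at 37/40, 101.8% at 38/40 and 102.3% at 39/40, and 40/40 would give 100% to 100%. The chance of 37 to 39 successes is 41% at p = 0.90 and 73% at p = 0.95; the chance of 40/40 is 1.5% and 12.9%.

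**The case against.** The strongest reply is that nothing rests on this interval. Feasibility turns on a count, and the exact table below the interval already gives a reader correct operating characteristics. That stands, and it is why the point is minor.

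A second reply is that the 4-point gap depends on the comparator. Exact and Wilson lower limits err the other way in this range (0.5% against 2.5% nominal). Jeffreys, whose lower-limit error averages 3.1%, sits only 80.7 − 78.0 = 2.7 points below Wald. This is fair as far as it goes: the gap is 3.8 to 4.4 points against the two methods named here and smaller against Jeffreys. The direction is the same for all three. Jeffreys coverage also dips to 88.6% within the range, so it is not a clear replacement.

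A third reply is that the sentence may describe how an observed proportion varies around an assumed true rate. The central 95% binomial range for X/40 is 80% to 97.5% at p = 0.90 and 35% to 65% at p = 0.50, so the printed lower limit would be only about 1 point off. But the text calls it a confidence interval, and that is how it will be read.

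Finally, the coverage figures describe Wald as a procedure applied to data, and the plan does not commit to reporting any interval. That limits the results above 100% to a conditional warning. It does not give the printed interval the 95% property it claims.

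**Conclusion.** The concern holds, at minor weight. The printed (81%, 99%) is a correctly calculated Wald interval, but the method is unnamed and poorly suited to 40 patients at a 90% success rate. Its lower limit is 4.4 points above exact and 3.8 above Wilson. Over the expected 90-95% range a nominal 95% Wald interval averages 88.7% coverage, with almost all of the error on the favourable side. The 50% example is essentially unaffected. The 35/40 rule, its table and the sample size are untouched.

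The conclusion assumes that the sentence means a confidence interval, as it says, that outcomes are independent binomial, and that the true rate lies in the range the plan expects. The limits above 100% and the zero-width interval at 40/40 arise only if Wald is also used for the final report, on which the plan is silent.

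**What to change.** In section 11.0, name Clopper-Pearson exact or Wilson as the interval method, both for the planning examples and for reporting the observed feasibility rate. Exact would match the section's binomial tables.

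- If exact: restate the 90% example as (76%, 97%) and the 50% example as (34%, 66%).
- If Wilson: restate the 90% example as (77%, 96%); the 50% example stays at (35%, 65%).
- Optionally, add the interval at the pass mark of 35/40: (73%, 96%) exact or (74%, 95%) Wilson.

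The cost is one method name and one restated interval, or two if exact is chosen. The stated lower limit becomes slightly less favourable. Exact is conservative (mean coverage 98.0% in the expected range), and Wilson falls slightly below 95% at some rates (minimum 93.5%). The pass mark, success table, sample size and safety stopping rule need no change.

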4.0 OVERVIEW OF STUDY DESIGN/INTERVENTION

4.1 Design

This feasibility study will aim to accrue 40 patients in one year or less. All patients who are consented for a total laparoscopic or robotic-assisted hysterectomy will be eligible for the trial, unless the surgeon does not plan to use a uterine manipulator. On average, the GYN Disease Management Team performs about 500 robotic and laparoscopic hysterectomies per year.

[name] and [name] will provide an educational training session to all GYN surgeons and fellows at an attending's meeting and/or a GYN Treatment Planning Conference prior

to protocol activation. All surgeons that will use the device will be provided with this training.

[name] will receive composite results to provide consulting guidance regarding the device and any further manufacturing. There will not be any PHI included in the information provided to him.

Contingent on successful completion of this trial, an application for FDA approval may be filed for this device.

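### The feasibility interval and the 35-of-40 table assume 40 independent cases although one surgeon may supply up to 8, so they may be too favourable if outcomes correlate within surgeon; the interval is also a Wald interval, optimistic near 90%

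*Combined protocol and SAP*

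**What the plan says.** Section 4.1 sets the size: "This feasibility study will aim to accrue 40 patients in one year or less". Section 11.0 gives the expectation, "We expect a very high percentage (90-95%) of patients to achieve successful docking", and illustrates precision with two 95% intervals for 40 patients: 35% to 65% at a success rate of 50%, and for the high rate, "if the hypothetical success rate is 90% then the confidence interval is (81%, 99%), assuming binomial proportions".

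The decision rule is "If the number of successes is less than 35 we will warrant re-design of the device and reassessment of its feasibility". A table of binomial probabilities supports it: "The table below provides the probability of observing at least 35 successes (>=35) out of 40 patients", for true rates from 0.5 to 0.9. The rows that matter most are 0.8 (0.16133) and 0.9 (0.79373).

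On surgeons, Section 6.0 says "The goal is to obtain 40 patients undergoing surgery from at least 8 of the 12 GYN surgeons", and Section 11.0 says "The maximum number of robotic manipulator uses per surgeon will be 8". Section 9.0 has the attending surgeon assess all outcomes. Nowhere do the documents mention correlation within surgeon, a design effect, or feasibility results by surgeon.

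**The concern.** A binomial calculation on 40 cases is right when the cases are independent with a common success probability. Here they are grouped by surgeon. The surgeon controls the arm and also records whether docking and manipulation succeeded, so operating skill and the threshold for calling a case a success are both shared within a surgeon. Positive correlation is therefore plausible, though the documents do not demonstrate it.

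Positive correlation would make the interval too narrow. It would also flatten the 35-of-40 rule: a device with a true rate of 0.7 or 0.8 would pass more often than the table shows, and one with a rate of 0.9 would be sent for redesign more often. That rule is the plan's only quantitative criterion for feasibility.

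A second point concerns the same interval. The normal-approximation (Wald) formula performs poorly for proportions near 1 at this sample size, whether or not there is clustering.

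**Working it through.** **Inputs.** From the documents: n = 40; pass at 35 or more; example success rate 90%, that is 36/40; cap of 8 uses per surgeon; goal of at least 8 of 12 surgeons. Assumed: ICC of 0.05 to 0.20, with values near 0 shown for comparison, because the documents give none.

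**Step 1: reproduce the stated figures.** Wald interval, p ± 1.96 × √(p(1 − p)/40):
- p = 0.5: 0.5 ± 0.155 = 34.5% to 65.5%.
- p = 0.9: 0.9 ± 0.093 = 80.7% to 99.3%.

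Both match after rounding. The binomial probabilities of at least 35 of 40 at true rates 0.5, 0.6, 0.7, 0.8 and 0.9 are 0.00000, 0.00014, 0.00862, 0.16133 and 0.79373, all as printed. The arithmetic in Section 11.0 is correct under independence.

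**Step 2: effect of clustering on the pass probability.** Each surgeon's success total is taken as beta-binomial with the stated mean and ICC, and the totals are convolved across surgeons. For 8 surgeons with 5 cases each, the design effect is DE = 1 + (5 − 1) × ICC and the effective sample size is 40/DE.

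| ICC | DE | Effective n | P(≥35) at 0.7 | P(≥35) at 0.8 | P(≥35) at 0.9 |
|---|---|---|---|---|---|
| 0 | 1.00 | 40.0 | 0.009 | 0.161 | 0.794 |
| 0.01 | 1.04 | 38.5 | 0.010 | 0.167 | 0.790 |
| 0.05 | 1.20 | 33.3 | 0.015 | 0.186 | 0.778 |
| 0.10 | 1.40 | 28.6 | 0.022 | 0.208 | 0.765 |
| 0.20 | 1.80 | 22.2 | 0.038 | 0.244 | 0.746 |

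Other layouts bracket this. At a true 0.8 and ICC 0.05 / 0.10 / 0.20:
- 12 surgeons with 3 or 4 cases each: 0.177 / 0.191 / 0.216.
- The most uneven split over 8 surgeons under the cap (8, 8, 8, 8, 5, 1, 1, 1): 0.198 / 0.228 / 0.275.
- 5 surgeons with 8 cases each: 0.203 / 0.236 / 0.285. The cap allows this, but it misses the 8-surgeon goal and is a worst case.

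**Step 3: separate the interval method from the clustering.** Lower 95% limits at 36/40, for 8 surgeons with 5 cases each. The exact (Clopper-Pearson) limits use beta quantiles on the effective n.

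| ICC | Wald | Exact |
|---|---|---|
| 0 | 80.7% | 76.3% |
| 0.05 | 79.8% | 74.6% |
| 0.10 | 79.0% | 72.9% |
| 0.20 | 77.5% | 69.8% |

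With no clustering, changing the method alone lowers the limit by 80.7 − 76.3 = 4.4 points. Clustering then takes off a further 76.3 − 74.6 = 1.7 points at ICC 0.05, 3.4 at 0.10 and 6.5 at 0.20. At an ICC of 0.10 or less, the method is the larger cause. The full exact interval at ICC 0 is (76.3%, 97.2%).

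**Step 4: does the repair help?** Simulated coverage of nominal 95% intervals, 8 surgeons with 5 cases each, true rate 0.9, ICC estimated by analysis of variance, design effect not allowed below 1:

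| ICC | Wald, n = 40 | Clopper-Pearson, n = 40 | Clopper-Pearson, effective n |
|---|---|---|---|
| 0 | 91% | 97% | 97% |
| 0.05 | 89% | 95% | 96% |
| 0.10 | 86% | 93% | 95% |
| 0.20 | 81% | 89% | 93% |

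**The case against.** The strongest reply is that a reader might infer more than the documents support, namely that the interval and the risk of passing a poor device are definitely misstated. Four points count against that stronger reading, and all four stand.

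- **No ICC is given.** Near zero the stated figures hold: at ICC 0.01 the pass probability at 0.8 is 0.167 against 0.161. Section 4.1 provides training for every surgeon who uses the device, which may reduce differences between them. Section 11.0 also discloses its binomial assumption.
- **The target of inference matters.** At least 8 of only 12 surgeons are sought. If conclusions are confined to those surgeons with fixed shares of the cases, differences between them do not inflate the error. With half the cases at 0.9 and half at 0.7, P(≥35) is 0.153, slightly below the binomial 0.161.
- **No unacceptable success rate is declared.** The 0.8 row is one line of a table and not a null hypothesis, so 0.161 is not a declared false-pass risk.
- **The interval is a planning illustration at a hypothetical rate.** Section 11.0 does not say that the final report will use this formula.

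The second point limits the concern without removing it. Shares are not fixed, since surgeries are scheduled by a sign-up sheet under a cap. The plan also looks beyond these surgeons: Section 4.1 mentions a possible application for FDA approval.

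It is also fair to say that formal cluster adjustment is weak at this size. With about 4 failures expected, the estimated ICC is zero or below in about half of simulated trials when the true value is 0.10. Most of the gain in coverage at low ICC comes from leaving the Wald formula.

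**Conclusion.** The concern holds in conditional form. The interval and the table assume independence that the design does not guarantee and the plan does not discuss. They may be too favourable if outcomes correlate within surgeon and the results are to apply beyond the participating surgeons. For 8 surgeons with 5 cases each and an assumed ICC of 0.05 to 0.20, the shift in pass probability is +0.03 to +0.08 at a true 0.8 and −0.02 to −0.05 at 0.9. This is modest at the low end and material from an ICC of about 0.10, or when cases concentrate in few surgeons.

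The Wald point needs no assumption about surgeons: at 36/40 the lower limit of 81% should be about 76% even with independent cases.

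This is a cheap improvement to the plan. It is not an error in the plan as written, and it gives no reason to change the sample size or the decision rule.

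**What to change.** In Section 11.0:

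- Specify that the final feasibility interval will be a Clopper-Pearson interval on the effective sample size, 40 divided by the surgeon design effect, with the design effect not allowed below 1. Name the ICC estimator.
- Restate the 90% example as (76%, 97%), labelled as ICC = 0.
- Report successes over attempts for each surgeon beside the interval.
- Footnote the 35-of-40 table as assuming ICC = 0, and add sensitivity rows for true rates 0.8 and 0.9 at ICC 0.05, 0.10 and 0.20 from the table in the working.

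Keep 40 patients and the 35/40 rule.

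The cost is some wording and a few lines of analysis. Uses per surgeon must already be counted to enforce the cap. The downsides are a wider interval and a very imprecise ICC estimate, which is why the counts by surgeon should always be shown with it.
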